**Prospective:**

- One evaluator will obtain all photographs to be evaluated in this study, examine Electronic Health Records, and collect necessary data and measurements onto a password protected Microsoft Excel Spreadsheet. Measurements to be recorded may include columellar angles, nostril width, nostril height, width of the lip cleft, etc. While most of the information can be gathered directly from the photographs, some factors may require calculations such as soft tissue ratios if need be. The primary investigator will be blinded to whether or not subject has participated in the DynaCleft® study. Data are to be measured twice and results compared to account for accuracy. Participants are identified on the spreadsheet solely by an assigned code. Factors to be recorded will also include general biographical and physical information (age, gender, weight, etc.), duration of treatment and compliance of caregivers.
- Interaction with

IRB NUMBER: HSC-DB-20-0311

participants in the DynaCleft® study will involve one monthly visit up until date of surgery, usually between 3 to 6 months of age. Each appointment is estimated to be

an hour long to allow for assessment of the orthopedic, recording of information, and addressment of any concerns. The initial and last visits may require more time due to obtainment of necessary photographs. Participants will be required to receive DynaCleft® treatment for at least 2 months before lip surgery to qualify. Additionally, parents of infants with incomplete unilateral cleft lip that choose not to use the DynaCleft® + Nasal Elevator system but are willing to complete the infant quality of life assessment at time of surgery will be allowed to complete the survey. All images obtained in this study will be stored in a password protected and encrypted computer. Prospective patient images will be stored in the Electronic Health Record. Images will be de-identified.

- Parents will be asked to complete the Infant and New Parent Quality of Life questionnaire at both the initial visit and date of surgery.

### **Data and Safety Monitoring**

- There are no adverse events expected as there is no direct risk involved with the participants. All patient information will be unidentifiable and stored in password protected devices.
- The DynaCleft® + Nasal Elevator system is an FDA approved medical device. Adverse events can include skin irritation from the adhesive tape. In the event of skin irritation, parents will be offered suggestions to limit irritation (including use of duoderm as a barrier between the skin and tape) or will be allowed to terminate their participation in the study.
- Unanticipated problems will be reported to the Center for the Protection of Human Subjects.
- Periodic assessment of research progression and data collection will be reviewed within the pediatric dental department through presentations and research committee meetings. Any deviations from protocol will be addressed with the research committee and appropriate authorities as necessary.

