### **Secondary Outcome Measures:**

- Quality of life assessment utilizing an Infant and New Parent Quality of Life questionnaire
  - Time points: initial time of examination with study team, time of surgery

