## **Ethics**

- IRB approval will not need to be sought from another IRB.
- The prospective aspect of this study will include a request for consent while the retrospective aspect will require a waiver of consent. To protect the privacy of participants, charts will only be accessed with a protected password on encrypted computers within a secure network, participants will be unidentifiable, any data stored will be on an encrypted computer, and individual information will solely be used for the purpose of this study.
- No risks to the safety of the patient or parent/guardian are anticipated with participation in this study. There is potential risk associated with the DynaCleft® + Nasal Elevator system, including skin irritation/allergy to the adhesive used in the system. If a skin allergy is encountered, participation in the study will be discontinued and appropriate care given. There is potential risk of breach of confidentiality with participation in this study, though all personal identifiers will be removed. Additionally, there is the risk that participants may tire or lose interest while completing the DynaCleft® + Nasal Elevator protocol.

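### The plan denies expected adverse events while naming skin reactions to the adhesive, and it pre-specifies no tolerability result or reason for stopping

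*Combined protocol and SAP*

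**What the plan says.** The Data and Safety Monitoring section opens with "There are no adverse events expected as there is no direct risk involved with the participants". Its second bullet turns to the device and says "Adverse events can include skin irritation from the adhesive tape". It adds that parents may end participation if irritation occurs.

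The Ethics section says "No risks to the safety of the patient or parent/guardian are anticipated with participation in this study". The next sentence names a potential device risk, "including skin irritation/allergy to the adhesive used in the system", and the section then says that an allergy leads to discontinuation from the study.

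The data to be collected are listed under Study Procedures, Prospective: "Measurements to be recorded may include columellar angles, nostril width, nostril height, width of the lip cleft, etc", and beyond these "general biographical and physical information (age, gender, weight, etc.), duration of treatment and compliance of caregivers". The same section sets a minimum of 2 months of device treatment before lip surgery for an infant to qualify.

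The primary outcomes are four photographic measures. The only secondary outcome is "Quality of life assessment utilizing an Infant and New Parent Quality of Life questionnaire". The Statistics section covers within-patient and between-group comparisons, the significance threshold and the 10-infant sample. It contains no safety analysis.

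**The concern.** The two sections that deal with risk each deny it and then name it. Neither denial is limited to the chart review. The one in Ethics speaks of participation, and consent is sought only for the prospective part.

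The inconsistency carries into the data plan. The reaction that the protocol foresees has no named place among the outcomes, the recorded factors or the analyses. This matters more here than in many device studies. The Background Information says that infants with incomplete cleft lip do not receive presurgical orthopedic therapy because the defect is milder, and that the device has not been studied in them. The alternative is therefore no device at all, and any effect on soft tissue has to be weighed against what the device does to the skin.

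The primary analysis is also exposed. Irritation may lead to withdrawal and allergy ends participation. If either happens before 2 months, the infant may not qualify, and the protocol specifies no record of the reason. The infants left for analysis would then be those who tolerated the tape.

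**Working it through.** **Step 1. Set the statements side by side.**

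| Section | Denial | Named risk | Stated consequence |
|---|---|---|---|
| Data and Safety Monitoring | no adverse events expected, no direct risk | skin irritation | parents may end participation |
| Ethics | no safety risks anticipated | skin irritation or allergy | allergy ends participation |

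In both sections the denial and the named risk cannot both hold for infants who wear the device.

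**Step 2. Look for a planned tolerability result.**

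- Primary outcomes: columellar angle, nostril width, nostril height, cleft lip width. No skin item.
- Secondary outcome: quality-of-life questionnaire. No safety endpoint.
- Recorded factors: soft-tissue measures, biographical and physical data, treatment duration, caregiver compliance. No skin item and no reason for stopping.
- Statistics: no safety analysis.

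Treatment duration and compliance bear indirectly on tolerability. Neither would tell a skin reaction apart from loss of interest, which the Ethics section also names as a risk.

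**Step 3. Follow an infant who reacts early.** The infant starts the device, has a reaction and stops before 2 months. Under the minimum-treatment rule the infant may not qualify. The protocol does not say what an infant must qualify for, or how those who stop early are analysed. As an assumed example, suppose 2 of the 10 infants stop this way and the others have no reaction. A count among all who started is 2/10 = 20%. A count among those who qualify is 0/(10 − 2) = 0/8 = 0%.

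**Step 4. What 10 infants could show if reactions were recorded.** The documents state no safety figure to reproduce and no event rate, so the counts below are illustrations. Input: n = 10 (Statistics section). Method: exact (Clopper-Pearson) two-sided 95% limits. For zero events the upper limit is 1 − 0.025^(1/n) = 1 − 0.025^(1/10) = 0.308.

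| Infants affected | Exact 95% interval |
|---|---|
| 0/10 | 0 to 30.8% |
| 1/10 | 0.3% to 44.5% |
| 2/10 | 2.5% to 55.6% |
| 3/10 | 6.7% to 65.2% |

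The chance of seeing at least one affected infant is 1 − (1 − p)^10. For assumed true rates p of 5%, 10%, 20% and 30% it is 40%, 65%, 89% and 97%.

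Ten infants can therefore show whether reactions are common, but cannot estimate the rate closely. These figures describe what recording would yield. They do not measure the size of the defect.

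**The case against.** The best defence is that the wording is loose but corrects itself at once. The first safety bullet goes on to data privacy, and other sections take the chart review before the prospective part, so that bullet may have been meant for the chart review. In both sections the device risk follows directly, and no careful reader would think skin reactions had been ruled out. The protocol also excludes infants with an adhesive allergy and states responses to irritation and allergy. All of this is fair. It makes the contradiction an editorial repair, but it supplies no data item and no analysis.

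A reader might infer that skin reactions will be neither recorded nor reported. The documents do not support that. The data lists are open-ended, the hour-long monthly visits leave room for recording information and dealing with concerns, and the evaluator also examines the health record. The study schedule, consent document and survey are listed as attachments but were not available for review, and any of them could hold a skin item.

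The reporting route for unanticipated problems does not settle the matter either. It says what goes to the institution's human-subjects office, not what the study captures or publishes.

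Two further inferences fail. Nothing shows that skin reactions would be the main cause of withdrawal: the Ethics section also mentions participants tiring or losing interest, and no section ranks the causes. Nor can one say that the trial would report benefit, since that depends on the results.

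What stands is the contradiction, and the absence of a specified tolerability result and reason for stopping from all the text that could be reviewed.

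**Conclusion.** The concern holds in a limited form. The contradiction in the two sections is plain on the text. In the reviewed material, skin reactions and reasons for discontinuation are not specified as recorded, counted or analysed, so the effectiveness results would stand without a pre-specified tolerability result. The minimum-treatment rule adds a selection problem: infants who stop early for a skin reaction can leave the analysed group unexplained, and among 10 infants even one or two such losses change who is analysed.

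This rests on two assumptions: that the unseen attachments hold no skin item, and that the 2-month condition governs entry to the analysis. The size of the problem cannot be stated, because the documents give no reaction rate. It should be corrected before the data are collected, but it does not invalidate the design.

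**What to change.** 1. Reconcile the sentences denying adverse events and risks, in Data and Safety Monitoring and in Ethics, with the device risks named beside them, or limit those sentences explicitly to the chart review.
2. Add to the recorded data under Study Procedures, Prospective, at each existing monthly visit: skin irritation or allergic reaction (yes/no, date, severity, whether device use or participation stopped), and the reason for any discontinuation. If the attachments already hold such an item, refer to it there.
3. In the Statistics section, plan a descriptive table beside the effectiveness results: the number of infants affected out of all who started the device, including those who do not reach 2 months, with an exact 95% interval. State that the interval will be wide.

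The denominator should be infants who started the device. Counting all enrolled could include some who were never exposed, and counting only those who qualify would drop the early stoppers. The skin item should be kept apart from the photograph measurements, because the evaluator is meant to be blinded when reviewing photographs.

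The cost is one line on the visit form and a short table, with no added visit.

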### **Statistics**

- Each individual patient will be monitored for changes during either participation in the experimental group or control group. A paired Student's t-test will be used to compare changes within the individual patient.
- Comparisons between the experimental and control group will be made with an appropriate statistical test depending on the distribution of data points (parametric or non-parametric).
- Up to 20 patients will be approached for recruitment for the prospective portion of this study. After the 10th patient is enrolled in the study, no other patients will be approached.
- We plan to enroll 10 subjects. This sample size collection was determined as an appropriate amount for a pilot study to test the effectiveness of this treatment. Similar studies using DynaCleft® have utilized similar sample sizes. Additionally, this number was based on the number of potential patients we can enroll within a twelve-month period.
- P-values less than 0.05 will be considered significant.

IRB NUMBER: HSC-DB-20-0311

- Termination of the pilot trial will occur after the 10th patient completes treatment.

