### General Information

This prospective study will investigate soft tissue changes of the DynaCleft® + Nasal Elevator system (CranioRehab, Denver, CO) on infants with non-syndromic incomplete unilateral cleft lip. The retrospective aspect of the study will examine records of infants who had or will have surgery without presurgical interventions and will provide as the control group. A comparison will be performed to analyze the effectiveness of DynaCleft® on soft tissues and on the quality of life for these infants and that of their families. Factors such as general physical appearances, overall development, behavioral differences, feeding improvements, and social functions will be evaluated. The study aims to use these collected data to establish the effectiveness of DynaCleft® for orofacial clefts at a university-based postdoctoral pediatric dentistry clinic.

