## **Study Design**

Newborns with incomplete cleft lip and parents that consent to presurgical intervention of DynaCleft® + Nasal Elevator system will be compared to a retrospective group of infants born with incomplete cleft lip treated by the UTHealth Texas Cleft-Craniofacial Team that have received surgical intervention and have existing presurgical photographs available for examination. The primary outcome will be to compare craniofacial soft tissue changes measured from extraoral clinical photographs obtained at the initial examination to the ones obtained prior to surgery. The child's guardian who completed the DynaCleft® therapy will also be asked to complete an infant quality of life assessment survey.

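### The Statistics section does not say that the between-group difference in change, rather than the paired t-tests, decides effectiveness, and growth can drive the paired tests for the three millimetre endpoints

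*Combined protocol and SAP*

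**What the plan says.** The analysis plan is the short list of bullets under Statistics. The first bullet covers both groups: "Each individual patient will be monitored for changes during either participation in the experimental group or control group". It then names its test: "A paired Student's t-test will be used to compare changes within the individual patient". The second bullet adds the contrast with controls: "Comparisons between the experimental and control group will be made with an appropriate statistical test depending on the distribution of data points". One threshold serves all of them: "P-values less than 0.05 will be considered significant". No bullet ranks the tests.

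Elsewhere the control comparison is clearly intended. General Information says "A comparison will be performed to analyze the effectiveness of DynaCleft® on soft tissues", and Study Design opens by saying that treated infants "will be compared to a retrospective group of infants born with incomplete cleft lip". The next sentence of Study Design, however, gives the primary outcome as to "compare craniofacial soft tissue changes measured from extraoral clinical photographs obtained at the initial examination to the ones obtained prior to surgery". That is a before-after comparison, and Outcome Measures lists the four primary endpoints as changes between the same two time points.

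Several sections bear on the time between photographs:

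- The title block gives a subject duration of four months for the prospective part.
- Study Design (Prospective) limits the intervention to three months, with the second photograph at the end of therapy just before surgery.
- Study Procedures (Prospective) requires at least 2 months of therapy.
- Background, Study Design (Prospective) and Study Procedures (Prospective) put lip surgery at 3 to 6 months of age.
- Study Population (Retrospective) lists the controls' photograph at repair at 3-4 months.

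Age and treatment duration are to be recorded. Photograph dates are not named, and the analysis does not use the interval.

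**The concern.** As the plan stands, a report could claim effectiveness from significant paired tests in the 10 treated infants and still comply with it. For three of the four primary endpoints that claim would be unsafe. Nostril width, nostril height and cleft width are lengths in millimetres, measured months apart in young infants. A paired change in such a length is growth plus any device effect, and the paired test cannot separate them.

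Background describes the effect seen with the device in complete clefts as a narrower and taller nostril. Growth would therefore imitate benefit for height and hide it for the widths. Soft tissue ratios might reduce the problem, but Study Procedures makes them optional and Outcome Measures lists none. No growth argument is made here for the columellar angle, although the missing ranking affects that endpoint too.

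The between-group difference in change removes growth that is common to both groups. It does so fully only if the photograph intervals are similar in the two groups, and the plan does not check this.

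**Working it through.** **Inputs.** From Statistics: 10 treated infants and a threshold of 0.05 (two-sided assumed). The documents give no growth rate, no SD of change and no number of controls. The SD of change is therefore set to 1, growth is varied, and 20 controls are assumed. The sample size of 10 has no power calculation behind it, so there is no planned figure to reproduce.

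**1. Growth alone in the paired test.** With mean drift d (in SD of change) and no device effect, the t statistic is noncentral with 9 degrees of freedom and noncentrality d × √10. It is significant when it exceeds 2.262 in absolute value. For d = 0.5 the noncentrality is 0.5 × 3.162 = 1.58.

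| Drift over the whole interval (SD) | Chance of p < 0.05 |
|---|---|
| 0.25 | 11% |
| 0.5 | 29% |
| 0.75 | 56% |
| 1.0 | 80% |

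Growth of 0.25 SD per month over 3 months is 0.25 × 3 = 0.75 SD, the third row.

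**2. Growth hiding a real narrowing.** Take a true narrowing of 1.0 SD, so the net mean is −1.0 + drift. With no drift it is detected 80% of the time. With 0.5 SD of drift (net −0.5) this falls to 29%, and with 0.75 SD (net −0.25) to 11%.

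**3. Paired tests in both groups are not a contrast.** With the same 0.5 SD drift and no device effect, the paired test is significant with probability 0.293 in 10 treated infants and 0.565 in 20 controls. One is significant and the other not with probability 0.293 × 0.435 + 0.707 × 0.565 = 0.53.

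**4. Unequal intervals in the between-group test.** The bias equals the growth rate times the gap in mean interval. For treated 3-4 months and controls 2.5-3.5 months, the means are 3.5 and 3.0, the gap is 0.5 month, and at 0.5 SD per month the bias is 0.25 SD. Without growth the standard error is √(1/10 + 1/20) = 0.387. The simulation used uniform intervals, linear growth, no device effect, a Welch test and 20 controls. All settings below stay within four months.

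| Treated (months) | Controls (months) | Gap in means | False positives at 0.25 / 0.5 / 1.0 SD per month |
|---|---|---|---|
| 2.5-3.5 | 2.5-3.5 | 0 | 5% / 5% / 5% |
| 2-4 | 2.5-3.5 | 0 | 5% / 5% / 5% |
| 2-3 | 2-3.5 | −0.25 | 5% / 6% / 9% |
| 2.5-4 | 2.5-3.5 | +0.25 | 5% / 6% / 9% |
| 2-3 | 2.5-3.5 | −0.5 | 6% / 10% / 22% |
| 3-4 | 2.5-3.5 | +0.5 | 6% / 9-10% / 22% |

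The sign depends on which group has the longer interval. A longer treated interval hides narrowing, and a shorter one imitates it. Regressing change on group and interval brings the rate back to about 5%, as it must when growth is simulated as linear.

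**5. Price of adjusting.** The SD of the adjusted group estimate is 0.395 when the intervals match (2% above 0.387) and 0.515 for treated 2-3 against controls 2.5-3.5 (0.515 / 0.387 = 1.33, so 33% wider). In that second setting, power for a constant 1.0 SD effect with no growth falls from about 69% to about 48%.

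**The case against.** A reader might infer that effectiveness will be judged on the paired tests alone. The documents do not support that. General Information ties effectiveness to the control comparison, Study Design opens with it, and Statistics plans a between-group test. Nor does any section propose to conclude from one significant and one non-significant paired result, so the 53% shows only why paired tests in controls would not rescue the inference. What stands is that the ranking is not stated and that the primary-outcome sentence points to the paired test.

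A reader might also infer that treated infants will be photographed much later than controls and that the between-group test is therefore seriously biased. With treated intervals of 2.5-5.5 months against 2.5-3.5, the false-positive rate would be 9% / 21% / 49% at 0.25 / 0.5 / 1.0 SD per month. That schedule exceeds both the four-month subject duration and the three-month limit on intervention. The 3 to 6 month age is the usual timing of lip repair in general, and both groups come from the same team. The documents allow different intervals but do not show them. Growth that slows with age would also reduce the figures for late photographs.

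Finally, one might want interval adjustment to decide every endpoint. That is a trade-off and not a correction. It costs power when intervals diverge, it absorbs part of an effect that builds with treatment time, and it has no growth rationale for the columellar angle.

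Pilot status does not remove the point, since the sample size is called an "appropriate amount for a pilot study to test the effectiveness of this treatment".

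**Conclusion.** The concern holds in a limited form and should be fixed. The missing ranking is a matter of text and needs no assumption about growth. Its consequence for the three millimetre endpoints is potentially large: with 10 infants and no device effect, a paired test is significant 11% to 80% of the time for drifts of 0.25 to 1.0 SD.

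The timing part is secondary and conditional. Within four months and with 20 controls, unequal intervals raise the false-positive rate of the unadjusted between-group test to at most about 10% at growth up to 0.5 SD per month, and to about 22% at 1.0. It stays at 5% when mean intervals match. All percentages rest on an assumed SD of change, assumed growth and, in the between-group case, assumed intervals and linear growth. They illustrate the mechanism and do not predict this study's error rate.

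**What to change.** Replace the first two Statistics bullets with:

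> For each primary endpoint, effectiveness is judged only by the between-group difference in change from the initial to the pre-surgery photograph, reported with a 95% confidence interval. Paired tests within either group are descriptive only and do not support a claim of effectiveness.

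The choice of between-group test can follow this text; it is a separate matter from the ranking. The primary-outcome sentence in Study Design should be brought into line.

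Record both photograph dates for every infant in both groups and report the distribution of intervals by group. For nostril width, nostril height and cleft width, add a sensitivity analysis that regresses change on group and days between photographs.

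The sponsor should reconcile the timing text in the title block, Background, Study Design (Prospective), Study Population (Retrospective) and Study Procedures (Prospective).

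The cost is wording, two dates per infant and one extra model. Control photographs are tied to identified visits and the evaluator already reads the health records, so the dates should be obtainable. The adjusted estimate will be less precise if intervals differ, and confounding from non-randomised controls remains.
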